Appendix 1. Randomized controlled trials evaluating percutaneous tibial nerve stimulation.

Study	Sample	Design	Intervention/Control	Outcome
OrBIT¹	100 adults with urinary frequency >8/day and OAB	Randomized controlled trial. Intention to treat.	PTNS (Urgent PC): 0.5-0mA, 20Hz, unilateral needle electrode, weekly 30 minute sessions x 12 weeks. Control: Tolterodine 4mg OD x 90 days	Intervention: 80% global response assessment moderate or markedly improved Sham: 55% global response assessment moderate or markedly improved. P<0.01
SUmIT²	220 adults with OAB	Randomized controlled clinical trial. Intention to treat.	PTNS (Urgent PC): 0.5-10mA, 20Hz, unilateral needle electrode, weekly 30 minute sessions x 12 weeks. Control: Sham group with identical setup but no active electricity.	Intervention: 55% global response assessment moderate or markedly improved Sham: 21% global response assessment moderate or markedly improved. P<0.001
PTNS versus placebo³	35 women with urodynamic DO and wet OAB	Randomized controlled trial. Intention to treat.	PTNS (Urgent PC): 0.5-10mA, 20Hz, unilateral needle electrode, 30 minute sessions 3x/week x 12 weeks. Control: Sham group with identical setup but no active electricity.	Intervention: 71% global response assessment moderate or markedly improved Sham: 0% global response assessment moderate or markedly improved. P<0.001
PTNS vs Oxybutynin vs Combination for OAB⁴	70 women with OAB	Randomized controlled trial.	PTNS (Urgent PC): 0.5-0mA, 10Hz, unilateral needle electrode, weekly 30 minute sessions x 12 weeks. Comparator 1: Oxybutynin SR 10mg PO OD x 12 weeks Comparator 2: Both PTNS and Oxybutynin x 12 weeks	Significant reduction among all groups, and no difference between groups based on ICIQ-SF score.

Appendix 2. Study schedule.

STUDY SCHEDULE	Visit 1 Screening	Visit 2 Randomization	Telephone Followup	Visit 3 End of study
Visit Windows	1- 4 weeks prior to Randomization	Week 0	Every 2-3 Weeks	12-13 Weeks
Documentation of Consent	X			
Medical History and Physical Exam	X			
Inclusion/ Exclusion Criteria Review	X			
Medication and Health Review	X			X
Urine Pregnancy Test	X			
PPBC Questionnaire	X		X (week 6-7 only)	X
OAB-q SF Questionnaire	X			X
3 day Voiding diary	Diary Provided	Completed diary returned & new one provided for Visit 3		Completed diary returned
24hr Urinary Pad test	Supplies Provided with instruction	Pads Returned & new ones provided for Visit 3	Pad test done 1-7 days prior to visit 3	Pads Returned
Randomization		X		
Initial 30 minute treatment session in clinic with nurse supervision		X		
Assessment of treatment masking			X (week 2-3 only)	
Assessment of compliance, review instructions, address any adverse events or questions			X	
Physician assessment of benefit				X

Appendix 3. Patient perception of bladder condition. Scored 0 (no problems) to 5 (severe problems).

(PPBC)

Which of the following statements describes your bladder condition best at the moment? Please mark “X” in one box only.

My bladder condition does not cause me any problems at all.

My bladder condition causes me some very minor problems.

My bladder condition causes me some minor problems.

My bladder condition causes me (some) moderate problems.

My bladder condition causes me severe problems.

My bladder condition causes me many severe problems.

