Study design: This is a randomized, double blind, sham controlled clinical trial. The primary intervention is 30 minute sessions, 3x/week, for 12 weeks of transcutaneous tibial nerve stimulation sessions carried out at home. The sham intervention will consist of the same treatment schedule, except with the application of transcutaneous nerve stimulation to the lateral aspect of the lower leg, away from the tibial nerve. Patients will undergo a 12 week treatment course. The patient and the treating physician will be blinded to the group assignment of the patient. Randomization will be done using a random number generator, and study assignment will only be released at the end of the study. Only the study nurse instructing the patient on placement of the study electrodes will know the patient assignment. The effectiveness of our sham protocol will be evaluated with a question during week 2-3 asking if they think they are in the active or sham group. The study visit schedule is outlined in more detail in Appendix 2.

Inclusion criteria

1. Female, >18 years of age, with the clinical diagnosis of overactive bladder (based on the current ICS definition²).
2. Failure of behavioral measures and pharmacologic therapy to adequately control overactive bladder symptoms.
3. Baseline patient perception of bladder condition score of 2 or higher.

Exclusion criteria

1. Current or previous percutaneous or sacral neuromodulation therapy
2. Stress predominant urinary incontinence

3. Newly added bladder medication or dose change with the last 2 months (Tamsulosin, Silodosin, Alfuzosin, Terazosin, Baclofen, Diazepam, amitriptyline, imipramine, DDAVP, tolterodine, oxybutynin, fesoterodine, darifenacin, solifenacin, trospium, mirabegron)
4. Intravesical botulinum toxin use within the last 1 year
5. Implanted pacemaker or defibrillator
6. History of epilepsy
7. Unable or unwilling to commit to study treatment schedule
8. Pregnant, or possible pregnancy planned for the duration of the study period
9. Active skin disease of the lower legs (dermatitis, cellulitis, eczema, trauma)
10. Documented allergy to patch electrodes or their adhesive
11. Abnormal sensory function of the lower limb
12. Metallic implant within the lower limb

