Intervention: Transcutaneous electrical nerve stimulation is a safe and effective therapy that has been used by physicians and other health professionals for a variety of conditions such as pain and muscle rehabilitation^{26,27}. We will use the EV-906 Digital TENS machine (from Everyway Medical Instruments Co Ltd, Health Canada License #73631). Two adhesive patch electrodes will be applied to one of the patient's lower limb, and the location used will be based on their treatment assignment (active treatment versus sham). The initial treatment will be carried out in the clinic under the supervision of the investigating physician, with training provided for the patient on proper use of the device by the study nurse. The remaining treatments will be detailed on a calendar for the patient, with telephone contact every 2-3 weeks with research staff to assess compliance. When undergoing active treatment, patients will have the electrodes applied posterior to the medial malleolus, and 5-10 cm above the medial malleolus of the same leg, just behind the medial tibial edge. As per previous studies involving transcutaneous posterior tibial nerve stimulation^{25,28,29} and similar to percutaneous tibial nerve stimulation²³, we will use the bipolar stimulation setting, with a frequency of 10 Hz, 200ms pulse, and the amplitude will be titrated up to patient's maximum nonpainful tolerance (between 0.5-10mA). For patients undergoing sham treatment, they will have the patch electrodes placed on the lateral side of the lower limb, and told to keep the current setting stable at 1mA. This will prevent any meaningful stimulation of the tibial nerve, while still delivering a slight tingling sensation to simulate active treatment.

Primary outcome measure: The patient perception of bladder condition (PPBC) is a commonly used measure for global response in overactive bladder studies. It is an ordinal scale from 0-5 (Appendix 3). It is a valid, reliable and responsive single question asking the patient to select the degree of problems associated with their bladder condition³⁰. Patients will be categorized as responders (score improvement by 2 points between screening visit 1 and end of study visit 3) or nonresponders.

Secondary outcome measures:

1. OAB related quality of life (OAB-q SF) Valid, reliable, and responsive tool for assessing symptom bother and OAB related quality of life³¹.

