2. 3-day voiding diary parameters (daily voiding frequency, functional bladder capacity, mean voided volume, longest time between voids, nocturia, number of urgency incontinence episodes). This is a valid and reliable measure of urinary symptoms³².
3. Quantification of urinary incontinence with 24hr pad weights. This is stable, reliable and responsive measure of the degree of urinary incontinence^{33,34}.
4. Physician assessment of benefit will be completed based on a standard clinical history at study visit 3 (end of study), and graded on a 7 point global response assessment.

Data Analysis and Sample Size

Analysis of our primary outcome will be an intention to treat analysis (using the chi squared test) based on the proportion of patients classified as a responder using the change in the patient perception of bladder condition. A secondary analysis, based on a per protocol analysis (for efficacy) will be performed for patients who completed at least 80% of the treatment sessions for at least 20 min each (determined from patient completed treatment diary, and electronic usage log in the TENS device). Secondary endpoints will be analyzed as appropriate using the students t-test or chi squared test. All data analysis will be carried out using SAS 9.2.

Using previous percutaneous tibial nerve stimulation studies as a guide²³, we estimate 20% of sham patients and 60% of actively treated patients will be responders. Using the Chi-square test, a two-sided alpha of 0.05, and 80% power, 27 patients per group will be required. Our final sample size, adjusting for a 10% dropout rate, is 60 (30 per group). Our sample size calculation is based on our intention to treat analysis.

References

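### Adverse-event questioning is scheduled only at the telephone calls and not at Visit 3, so the last weeks of home stimulation may have no scheduled adverse-event question

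*Combined protocol and SAP*

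**What the plan says.** The Study design section describes the treatment as "30 minute sessions, 3x/week, for 12 weeks of transcutaneous tibial nerve stimulation sessions carried out at home". The Intervention section places the first session in the clinic and provides for "telephone contact every 2-3 weeks with research staff to assess compliance"; it does not mention adverse events as a purpose of those calls.

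Adverse events are named once in the document, in the Appendix 2 row "Assessment of compliance, review instructions, address any adverse events or questions". That row has a single mark, in the telephone column, where the interval is "Every 2-3 Weeks". It is blank at Visit 3, which falls at week 12 to 13.

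Two other items at Visit 3 come near the subject. The row "Medication and Health Review" is marked at Visit 1 and again at Visit 3. The fourth secondary outcome reads, in part, "Physician assessment of benefit will be completed based on a standard clinical history at study visit 3 (end of study"; the result is graded on a 7-point scale.

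The outcome sections list no safety outcome, and Data Analysis and Sample Size describes no safety analysis.

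**The concern.** After the first session, patients stimulate themselves at home, so the scheduled contacts are the main planned source of information on harm. If the last planned adverse-event question comes at a telephone call some weeks before treatment ends, a reaction that starts or persists after that call is recorded only if it happens to come up at Visit 3.

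The protocol itself treats local skin problems as relevant. It excludes patients with active lower-leg skin disease and patients with "Documented allergy to patch electrodes or their adhesive". The second criterion can remove only an allergy already on record, so a first reaction could occur during the study.

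The arms also differ in electrode site and in current: the active arm is titrated to what the patient can tolerate without pain, and the sham arm is held at a fixed low setting. Event rates may therefore differ between arms, and a collection window that closes early would weaken any comparison of tolerability. The primary and secondary efficacy comparisons are not at stake.

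**Working it through.** The plan gives no figure on this point, so there is none to reproduce. The check is a reading of the schedule followed by a calendar count.

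**1. What is marked at Visit 3.** The marked or completed rows are the medication and health review, the PPBC, the OAB-q SF, return of the diary and pads, and the physician assessment of benefit. The adverse-event row is blank. Because other rows do carry marks in the Visit 3 column, the blank is unlikely to come from text extraction. The physical examination row is marked at Visit 1 only.

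**2. Inputs for the count.**
- Three sessions a week for 12 weeks (Study design): 3 × 12 = 36 sessions.
- Calls every 2 to 3 weeks (Intervention; Appendix 2).
- Visit 3 at week 12 to 13 (Appendix 2).

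**3. Formulas.** Let L be the week of the last call before week 12. Sessions after that call = 3 × (12 − L). Share of treatment = 3 × (12 − L) / 36. Weeks from the last call to Visit 3 = 12 − L to 13 − L.

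| Call spacing | Call weeks | L | Sessions after L | Share of 36 | Weeks to Visit 3 |
|---|---|---|---|---|---|
| Every 2 weeks | 2, 4, 6, 8, 10 | 10 | 3 × 2 = 6 | 17% | 2 to 3 |
| Every 2.5 weeks | 2.5, 5, 7.5, 10 | 10 | 3 × 2 = 6 | 17% | 2 to 3 |
| Every 3 weeks | 3, 6, 9 | 9 | 3 × 3 = 9 | 25% | 3 to 4 |
| Uneven: 2.5, then 3, 3, 3 | 2.5, 5.5, 8.5, 11.5 | 11.5 | 3 × 0.5 = 1.5 | 4% | 0.5 to 1.5 |

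Regular spacing thus leaves 17% or 25% of sessions after the last scheduled question. Uneven spacing within the allowed interval left between 0.5 and 3 weeks in the patterns tried. The 2-weekly and 3-weekly series would both reach week 12 at their next step; a call made then would close the gap, but the document does not fix the timing of the last call.

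**4. Whether another Visit 3 item fills the gap.** The health review is also marked at Visit 1, before any stimulation; its content is not defined, and it stands apart from the row that names adverse events. The clinical history is described as the basis for grading benefit. Either could elicit a late event. Neither is specified to do so.

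**The case against.** The strongest reply is that Visit 3 is not empty. A health review done at baseline and repeated after treatment can naturally be read as a check on what has changed, and a physician takes a history on the same day. A reader might infer from the schedule that patients are never asked about late reactions, or that such events cannot be captured. The documents do not support that: the content of the review is undefined, which leaves the question unspecified but does not rule it out. The consent pages are also not in the text, so instructions to patients on reporting problems cannot be assumed absent.

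A second reply is that 17% to 25% depends on evenly spaced calls with none at week 12. That is correct; the gap can be as short as about half a week. A reader might also take these percentages as the share of adverse events lost. That would require events to be spread evenly over treatment and all late ones to be missed at Visit 3, and nothing in the documents supports either.

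A third reply is that the plan has no safety objective or safety analysis and that both arms follow the same schedule, so no efficacy result is biased. This also stands. It limits the consequence to what can be said about tolerability.

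None of these replies shows an adverse-event question scheduled at the end of treatment.

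**Conclusion.** The point holds as a gap in the schedule. Adverse-event questioning is planned at the calls and not at Visit 3, and no other section supplies it. With regular call spacing, 6 of 36 sessions (17%) or 9 of 36 (25%) follow the last scheduled question; uneven spacing can make this smaller. Late or unresolved events could be missed, and a tolerability statement could be too favourable. It does not follow that such a statement would be too favourable, because the Visit 3 review and history may pick events up and the size of any undercount is unknown.

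The sample size, the primary outcome and the secondary efficacy analyses are unaffected. The change is worth making because the remedy is cheap and uses a visit that already takes place.

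**What to change.** In Appendix 2, mark adverse events since last contact at Visit 3 as well as at the calls. Alternatively, add one sentence stating that the Visit 3 health review includes this question.

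Specify who asks and when. Electrode position reveals the assignment, and the treating physician is meant to be blinded. The question and any check of the electrode site should therefore be done by the study nurse who already knows the assignment, after the PPBC and the physician assessment are complete, so that neither outcome is influenced.

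Add a line to the analysis section that adverse events will be reported descriptively by arm over the full 12 weeks.

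The cost is a few minutes at an existing visit and one descriptive table, and a few more minor events will probably be reported. No additional visit or patients are needed.
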